#### 4.1 Study Duration

The research study duration is planned four years after IRB approval, 8/31/2026.

#### 4.2 **Outcome Variables/Endpoints**

**Outcomes and measures.** We have identified measures and sources of data for each element in our conceptual model and have mechanisms in place to collect the data at key points throughout the study.

**Community outcomes and measures:** *i) FCS built into services system:* We will count number of people trained, number of people fitting description of target group accessing services at the NH-FE , asking about the issue at annual focus groups with service providers, at quarterly AB meetings and annual stakeholder and community meetings. *ii) Reduced discrimination among bank staff regarding mental illness and criminal justice involvement.* We will count number of people trained, ask at annual focus groups with bank and credit union leaders staff if they have noticed different attitudes towards and treatment of target group, and ask at quarterly AB meetings and annual stakeholder and community meetings if they have noticed different attitudes towards and treatment of target group; *iii) More financial products that meet needs of formerly incarcerated people with mental illness.* We will track product offerings through visiting calling branches, ask about products at annual focus groups with bank and credit union leaders staff, and ask at quarterly AB meetings and annual stakeholder and community meetings whether people have noticed improved product offerings; *iv) More community collaborations.* We will document community collaborations and partnerships working towards policy and legal reform created as a result of the project and monitor and document the activities of those partnerships. Due to a lack of a randomized trial for the community level interventions, we plan to conduct a pre-post analysis, e.g., use a pair analysis to determine if there are differences between baseline (pre-intervention) and during follow-up (post-intervention). We will also consider the use of segmented regression, separating the time periods into segments based on key events happening (i.e., trainings offered) and analyze changes over time. For outcomes for which we are able to obtain "control" data (state level data on recidivism), we will employ a difference-in-difference approach to help ensure that the impact being observed can be attributed to the intervention and not just a temporal trend. **Societal outcomes and measures:** Any policy legal reforms resulting from the improved community collaborations may be beyond the scope of this grant, given the time such changes take. We will document community meetings and activities and will monitor the progress of any legal or policy reform.

**Individual outcomes and measures:** Based on statistical power analysis (described below), we will recruit up to 204 participants. Potential participants will be given study information, including a contact number. On calling, they will be screened for eligibility, and given study information. If they are interested in participating, a meeting will be arranged at which, after obtaining written informed consent, they will be administered the baseline interview packet and paid \$50 for completing the interview. They will then be referred to the NH-FE for FS support peer support. Participants will also complete the interview measure packet at 6-month and 12-month follow-up. Financial situation (see measures below) will, for people engaged in FS, be measured using the NH-FE existing data monitoring system, Financial Empowerment enter Boost Outcome Tool (FE BOT), which we have permission to access for study participants. **Qualitative component:** A sub-sample of 18 participants, selected randomly, will be invited to participate in in-depth qualitative interviews at baseline, 6-month, and 12-months. Interview guides will be developed to probe specific issues identified through community and AB meetings; the content of this guide may change over time based on the results of ongoing quantitative and qualitative data collection, and in discussion with the AB. Interviews will last between 45 minutes to 1 hour, and participants will be paid \$50. All in-depth interviews will be audio-recorded and transcribed. **Participant Observation.** We will add context to our understanding of the interview data through adapted participant observation methods. We will use tools adapted from ethnographic methods, such as focused ethnography and rapid-Assessment Ethnography to obtain 'thick description. For example, we will spend time with participants before and after coaching sessions and will take detailed, reflexive notes, though we will not participate in coaching sessions. We will spend time in spaces and institutions pertinent to the financial lives of our target group, identified through meetings with the advisory board and the BP process, and take detailed field notes.

#### 4.2.1 Primary Outcome Variables/Endpoints

**Primary outcomes:** Target mechanisms to be measured include financial skills, financial self-efficacy, and financial behavior. Primary outcomes include financial situation (use of financial products, income, current debt, savings, credit score, financial hardship), financial well-being, employment, housing, social support, sense of belonging, and mental health supports.

Financial capability support (FCS) as part of general service system:

We will measure this outcome by counting number of people trained, number of people fitting description of target group accessing services at the NH-FEC, asking about the issue at annual focus groups with service providers, and at quarterly CAB meetings and annual stakeholder and community meetings.

Discrimination of bank staff:

We will measure this outcome through counting number of people trained, asking at annual focus groups with bank and credit union leaders/staff if they have noticed different attitudes towards and treatment of target group, and asking at quarterly CAB meetings and annual stakeholder and community meetings if they have noticed different attitudes towards and treatment of target group.

Access to safe and affordable financial products:

Indicated by:

Greater availability of existing products and introduction of new products

Measured by (quantitative):

- Track product offerings at local banks/credit unions through observation and call to local branch managers (annual years 1-4)

Measured by (qualitative):

- Focus group with bank and credit union leaders (annually years 1-4, representatives of approx. 10-15 institutions)
- CAB/CBPR meeting notes (ongoing - CBPR community/stakeholder meetings will be held at least annually. CAB meetings will be held quarterly).

Effective community collaboration:

Indicated by:

Partnerships created, meetings held, bills supported Measured by (qualitative):

- Research team meeting notes (ongoing)
- CAB/CBPR meeting notes (ongoing - CBPR community/stakeholder meetings will be held at least annually. CAB meetings will be held quarterly)
- Media tracking.

Use of safe and affordable financial products:

From Administrative data from the Financial Empowerment Center Boost Outcome Tool (FECBOT) and by self-report (do you currently have a bank account? Does your account allow for charging of overdraft fees?).

Debt:

From Administrative data from the Financial Empowerment Center Boost Outcome Tool (FECBOT), self-report (please list all the debts you currently owe) and as part of a validated measure of financial hardship.

Credit score:

From Administrative data from the Financial Empowerment Center Boost Outcome Tool (FECBOT) and by self-report (what is your current credit score - select from range).

Income:

From Administrative data from the Financial Empowerment Center Boost Outcome Tool (FECBOT) and in the Lehman (1988) Quality of Life interview

Financial well-being:

1) A validated measure of financial stress, the Incharge Financial Distress/Financial Well-being Scale (IFDFW) Scale

(Prawitz 2006)

2) A validated financial well-being measure which assesses a person's feelings about aspects of their financial situation (CFPB 2017)

Employment:

We will measure employment as well as satisfaction with employment with the Lehman (1988) Quality of Life interview, which has established reliability and validity.

Housing:

We will measure housing as well as satisfaction with living situation with the Lehman (1988) Quality of Life interview, which has established reliability and validity.

Social support:

We will measure social support using the ISEL-12 scale. This 12-item scale has established reliability and validity.

Mental health supports:

In our self-reported Service Use measure, participants will be asked about the number of visits for outpatient mental health services, self-help groups, peer support, social rehabilitation, and supported employment.

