**Our team has led research showing strong evidence of the value of peer support as a bridge between social inequities and optimal health.** Our team has been on the forefront of developing and evaluating peer interventions since the 1990s, demonstrating that those who have "been there" can serve as powerful motivators, role models, and educators for others. Peers can effectively engage people who have been otherwise difficult to engage, connect them to needed services, while instilling hope, and promoting activation and self-care. In our research, peer interventions have been associated with moderate to large effect size improvements among persons with serious mental illness in: hope, sense of well-being, self-care, and quality of life; drug and alcohol use and hospitalizations; and community tenure after hospitalization. Meta-analyses and systematic review show that peer-delivered services are generally equivalent to usual care conditions for adults with SMI in regard to traditional clinical outcomes (e.g., symptom severity), and superior to usual care when examining more recovery-oriented outcomes (e.g., hope, empowerment, quality of life). Research by [name] with Black and Latinx people with Substance-Use-Disorder (SUD) indicates that Imani, a peer support and community health worker (church facilitators) driven intervention can impact overall wellness (the 8 dimensions of

[figure not shown]

Figure 1: Results of Imani project

wellness), including improvements in financial health from baseline to 12 weeks following the intervention (see figure 1). To date, over 1000 individuals have enrolled in the Imani program across the state of T; Imani participants across 7 sites were from diverse backgrounds and experiences: 43% female, 22% Latinx, and 61% Black. The majority had experienced incarceration (65%), and 14% were on probation parole. Data collected from cohorts 2 and 3, found 43% of those who began treatment were retained at weeks 12 and 32% were retained at week 22. In addition, we found a significant increase in all 8 scores on the Dimensions of Wellness assessment from pre- treatment to week 12 (time p <.05). This work indicates that peers can be effective in working with people to address SDOH and other experiences resulting from structural discrimination.

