***Our team has conducted research on peers for justice-involved people with mental illness:*** [name] work has also focused specially on the training, development, and implementation of Forensic Peer Support (FPS) services. People with histories of mental health and SUD challenges returning to the community after incarceration face tremendous challenges in successful reentry to community, including reconnecting or connecting with mental health and substance abuse treatment, finding adequate housing, finding employment, reuniting with family and friends, dealing with finances, etc. Recidivism remains high principally because of these challenges. FPS can help people connect with their communities, access treatment and other supports, and assist with psychological, social, and financial challenges, and in so-doing can reduce recidivism substantially. Peer support may help with confidence and self-esteem when dealing with financial challenges. In previous research conducted by [name] and colleagues on the PeerStar forensic peer project for people with mental health and SUD challenges returning from jails in rural Pennsylvania, all had a mental illness diagnosis. Surprisingly, in the first year after release from prison, participants did much better than those in the general US prison population in terms of re-incarceration rates (21.7 percent vs 43.4 percent). While preliminary findings of this approach, this study reaffirms the idea that forensic peer support can help reduce recidivism rates for people diagnosed with a mental illness coming out of prison.

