intervention will affect community-level health determinants including: i) more availability of services (integrating financial capability support into the existing service environment); ii) less local structural discrimination (by bank staff against justice-involved people who have mental illness); iii) more community resources (access to safe, affordable financial products, effective community collaborations working towards legal/policy reform). Resulting individual level outcomes will include improved financial well-being, which will improve recidivism and health outcomes directly, and indirectly through improving employment and housing outcomes, increasing sense of belonging, and strengthening social network and mental health supports.

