### 3.3 Objectives

This research project will use Community Based Participatory Research (CBPR) methods to achieve the following specific aim:

- 1) Change community level determinants that impact financial well-being and health of the target group by training existing service provider including: i) community-based financial capability providers to be able to address financial difficulties of the target group; ii) service providers along the criminal justice pathway to be able to provide basic financial guidance to target group; iii) financial institution staff to reduce discrimination related to financial consequences of justice-involvement and mental illness. We will also support community collaborations working for legal/policy reform that impacts finances of target group.
- 2) Use mixed methods to assess impact on community determinants, measuring integration of financial capability support into existing services, ability of financial coaches to support target group, access to financial products, attitudes, knowledge and behavior of bank staff, strength of community collaborations, and progress towards changes in laws and policies.
- 3) We will assess impact on individuals by measuring target mechanisms (financial skills, self-efficacy and behavior) hypothesized to mediate the relationship between financial capability support and primary outcomes including financial well-being and other health determinants (employment, housing, social support, mental health supports, and belonging), secondary outcomes (health and recidivism) and mediators between primary and secondary outcomes (hope, empowerment, and mastery).
- 4) Assess the value of integrating peer support into community-based financial capability support for the target group by randomizing participants into two groups, financial capability support only, or financial capability support plus peer support.

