Participants will be randomized to two arms: Arm #1 financial capability support = a) one-on-one financial coaching, which entails monthly or more frequent meetings with a financial coach; initial meetings are in person, and subsequent meetings can be via zoom, phone or in person, depending on the convenience for the client and b) access to safe and affordable financial services, which includes support with managing any existing bank accounts, or supporting a person to open a new overdraft-free account. Coaches can also help people to access other financial products such as free tax preparation (VITA), credit builder loans, online bank accounts, or other products recommended by our Justice Tech partner.

Arm #2 with peer support = in addition to financial capability support will also be offered one-on-one peer support from a trained Recovery Support Specialist...during the period they are receiving the intervention. Wellness coaches will provide weekly meetings (30 to 60 minutes duration).

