### 6.2 Method of Assignment/Randomization (if applicable)

Randomization will take place at the individual level. Participants will be randomized to treatment as usual (regular FCS) or treatment as usual with peer support using a 1:1 allocation ratio. The randomization scheme will be generated by the study statistician and given to the data manager for implementation using the Research Electronic Data Captures (REDCap's) randomization module to maintain allocation concealment. The randomization will be stratified by gender and carried out using random permuted block sizes of 2,4, and 6. Participants will be randomly allocated after completion of the baseline assessment.

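### The mental health supports outcome counts peer-support visits, the service that only Arm 2 is randomised to be offered, and does not exclude study sessions

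*Protocol*

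**What the plan says.** Section 4.2.1 ends its list of primary outcomes with "sense of belonging, and mental health supports". The same section defines the last of these through a self-reported service-use measure in which "participants will be asked about the number of visits for outpatient mental health services, self-help groups, peer support, social rehabilitation, and supported employment". Section 6.1.1 has the interview packet completed at baseline, 6 and 12 months.

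Section 6.2 sets the randomised contrast: "Participants will be randomized to treatment as usual (regular FCS) or treatment as usual with peer support using a 1:1 allocation ratio". Section 4 gives the contact frequency for Arm 2: "Wellness coaches will provide weekly meetings (30 to 60 minutes duration"). It ties the length of peer support to the period of intervention and gives no number of weeks.

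Section 6.1.1 includes a Peer Support Provider Contact Log in the packet, but no section connects it with this outcome. No section restricts the item to services outside the study, asks participants to leave out study sessions, or removes the item from the between-arm comparison. The protocol does not say whether the five counts are summed or analysed one by one.

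Section 7.1 bases the primary hypothesis and the sample size on financial well-being.

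**The concern.** An outcome used to judge an intervention should not contain the delivery of that intervention. Here one of the five counted services is the randomised treatment. Any study session that a participant reports counts as outcome, and only Arm 2 is offered such sessions.

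If the counts are summed, the total is biased towards Arm 2. If they are analysed separately, the problem is confined to the peer-support item, which then mostly measures treatment receipt.

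Aim 4 in Section 3.3 is at stake: "Assess the value of integrating peer support into community-based financial capability support for the target group". Section 1.2 gives the rationale that peers engage people and "connect them to needed services", and says of forensic peer support that "FPS can help people connect with their communities, access treatment and other supports". Section 2.3 expects benefit partly through "strengthening social network and mental health supports". A count that includes the peer sessions cannot show that peers connected anyone to other services, because it can favour Arm 2 when no such connection occurred.

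**Working it through.** **The plan's own figures.** A two-sample t-test for 0.5 SD, two-sided alpha 0.05 and 90% power needs 85.03 per arm, so 86. Then 86/0.85 = 101.2, so 102 per arm and 204 in total. At alpha 0.01 and 80% power the detectable effects are 0.526 SD (N = 172) and 0.557 SD (N = 154). All agree with Section 7.1 (86, 204, 0.53, 0.56). None of them is in dispute.

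**Inputs from the protocol.** Weekly sessions (Section 4); 86 per arm at 6 months and alpha 0.01 for outcomes other than the main one (Section 7.1).

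**Assumptions.** The protocol does not state the recall window, duration of contact, attendance or SD. I take W = 26 or 12 weekly sessions in the window; a share p = 25% or 50% of Arm 2 attending and reporting all of them, the rest none; SD of other visits s = 10, 20 or 30; and no effect on other services.

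**Formulas.** Added visits in Arm 2 = W·p. Arm 2 variance = s² + W²·p(1−p). Standardised artefact d = W·p / √[(2s² + W²·p(1−p))/2]. Chance of rejection = Φ(d·√43 − 2.576), where 43 = 86/2.

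**Worked case, W = 26, p = 0.25, s = 10.** Added visits = 6.5. W²·p(1−p) = 676 × 0.1875 = 126.75. Denominator = √[(200 + 126.75)/2] = 12.78. d = 6.5/12.78 = 0.51. Chance of rejection = Φ(0.509 × 6.557 − 2.576) = 78%.

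**(a) Summed count**

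| Weeks | SD | d at 25% / 50% attendance | False-positive chance at 25% / 50% |
|---|---|---|---|
| 26 | 10 | 0.51 / 0.96 | 78% / >99% |
| 26 | 20 | 0.30 / 0.59 | 28% / 90% |
| 26 | 30 | 0.21 / 0.41 | 11% / 56% |
| 12 | 10 | 0.28 / 0.55 | 23% / 85% |
| 12 | 20 | 0.15 / 0.29 | 5% / 26% |
| 12 | 30 | 0.10 / 0.20 | 3% / 10% |

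All-or-none attendance is not the worst case. If every Arm 2 participant gained the same 6.5 visits (W = 26, s = 10), d would be 6.5/10 = 0.65 and the chance 95%.

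**Attendance at which the artefact alone equals the plan's detectable 0.53 SD.** Over 26 weeks: 26%, 45% and 64% at SD 10, 20 and 30 (on average 6.8, 11.7 and 16.6 study visits per Arm 2 participant). Over 12 weeks: 48% at SD 10, 89% at SD 20, and out of reach at SD 30, where full attendance gives only 12/30 = 0.40.

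**Skewed counts.** Simulation with negative binomial counts (assumed mean 10, SD 10, t-test, 4,000 trials) rejected in 77.5% (W = 26, p = 0.25), 22.5% (W = 12, p = 0.25) and 83.8% (W = 12, p = 0.5), in line with the formula. Without study sessions it rejected in 1.1%.

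**(b) Peer-support item alone, 25% attendance, item SD assumed 3, 5, 8.** Over 26 weeks d = 0.76, 0.69, 0.58 (rejection 99%, 98%, 88%). Over 12 weeks d = 0.63, 0.48, 0.34 (94%, 72%, 37%). These rejections are not type I errors: they detect a real difference in peer support received, which is delivery of the treatment and not its effect.

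**The case against.** The strongest reply is that scoring a service-use form is usually left to the analysis plan or the form instructions, so silence on summing and on study contacts is not an error. That holds for the scoring. It does not hold for the content: Section 4.2.1 names the services counted, and the randomised treatment is one of them. Both ways of scoring are affected, one in the total and the other in a single item.

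Second, the outcome's rank can be disputed. Section 7.1 makes financial well-being the primary outcome of interest and treats several others from the Section 4.2.1 list as secondary, with false-discovery control in Section 7.2. This stands, and it limits the damage to one listed outcome.

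Third, peer support received is itself a mental health support, so total support is a defensible quantity. As a description it is. As a comparison of arms it partly restates the allocation.

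Fourth, Section 2.3 links stronger mental health supports to better financial well-being and not to peers specifically. That is fair, and the argument rests more on Section 1.2 and aim 4.

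Fifth, every magnitude input is assumed. Participants may not report all sessions under this item, and study sessions may replace outside visits. The calculation is a single 6-month contrast, whereas Section 7.2 plans mixed models that average over time unless the interaction is significant. All of this stands. It makes the size uncertain but does not remove the direction of the bias in a summed count unless replacement is complete or study sessions go unreported.

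**Conclusion.** The concern holds. As written, the between-arm comparison on mental health supports includes receipt of the randomised treatment. Over the assumed ranges, the artefact in a summed 6-month count runs from 0.10 to 0.96 SD, with a 3% to over 99% chance of a false positive at alpha 0.01: from negligible to decisive. It may be absent at 12 months if sessions end before the recall window opens. Arm 1 may also obtain peer support elsewhere, which would count in either arm.

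The main test on financial well-being and the sample size of 204 are untouched. The definition should be corrected, but the flaw does not threaten the trial's central conclusion. Confidence in the definitional flaw is high. Confidence in its size is low, because attendance, SD, duration, recall window and summing are not stated.

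**What to change.** In Section 4.2.1, define the between-arm outcome as visits to the other four service types, each or in total, and align the analysis wording in Section 7. Leave the peer-support item out of the between-arm test and report it descriptively by arm, which keeps the information on outside peer support in Arm 1. Report study peer contacts from the Peer Support Provider Contact Log as Arm 2 exposure.

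The cost is one outcome definition and the matching analysis text. No new data are needed, since the service-use items and the log are already planned. The drawback is that peer support from outside the study drops out of the between-arm test.

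The item itself should not be reworded mid-trial unless comparability with data already collected is preserved. Section 4 has enrolment running from month 9 of year 1, and a change of wording could make baseline and follow-up counts non-comparable.
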